### 5.2 Sensitivity analyses

For the primary endpoint analysis, an evaluation with the negative binomial distribution to detect a possible but not expected overdispersion will be performed.

Further, for both primary and key secondary endpoints, per protocol analyses as well as adherence analyses based on NH and resident level will be performed.

Finally, an adjusted analysis is performed taking into account remarkable (p < 0.05) differences at baseline and t1, regarding the following potential confounders:

20

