## 2 Study Methods

## 2.1 Trial design

BEVOR is a two-arm, parallel group, prospective, multicenter, cluster randomized controlled trial (cRCT). Nursing homes and related health care providers form the clusters and they themselves (DC1) or, respectively, their residents (DC2) the observation units. The allocation ratio of the clusters is 1:1 for the two groups:

- ACP program (experimental treatment group):
   Each nursing home and related care providers will receive an institutional and regional implementation of the complex German ACP program including a ACP facilitator .
- Care as usual (control group): For each nursing home and health care provider all common care options within the German health care system are available. The control group will receive a delayed ACP intervention after final data collection.

The trial is observer blinded (outcome assessors (until finalization of the SAP) and data collectors are blinded).

44 nursing homes with an average of 96 residents each, from the 4 study centres in Düsseldorf (2 regions), Munich (2 regions), Halle (2 regions) and Göttingen (2 regions) are participating.

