### 2.2 Randomization

A 1:1 cluster-randomization at the level of NHs stratified by study center and region for experimental and control group was carried out using a computer-based code with variable block sizes with length 2 to 4 (to ensure intervention NHs in every region since it has been promised to the NHs) within each stratum. The randomization list was created by a research associate of the Institute for Medical Biometry and Epidemiology of the University Medical Center Hamburg-Eppendorf, who is not directly involved in the implementation of the research project using R version 3.6.2.

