### 2.3 Sample size

To be allocated to trial: 44 NHs (22 per group) including on average n = 100 residents each, resulting in a target sample size of n = 4.400 (2.200 per group) enrolled patients in total.

To be analysed: n = 1760 residents in 22 NHs per group and n = 3520 residents in 44 NHs in total. Full details of sample size calculation can be found in the study protocol [2].

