## 3 Statistical Principles

### 3.1 Confidence intervals and P values

All applicable statistical tests will be two-sided and at a 5% significance level. Analyses of secondary outcomes will be performed without adjustment for multiplicity. All confidence intervals presented will be 95% and two-sided.

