### 5.1.2 Primary Outcome

The primary analysis is performed in the ITT population at NH level. For rate comparison a Poisson regression model is calculated taking into account group (intervention vs control) as independent variable, realized follow-up time as offset, region of NHs and the respective baseline hospitalization rate as covariates. The treatment effect is presented as incidence rate ratio (IRR) with corresponding 95%-Confidence interval (CI) and p-value. Marginal estimators (numbers per 100 residents per past 12 -months observation period (from t1 to t2)) with corresponding 95%-CI are given per treatment group.

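### If homes vary beyond Poisson, the negative binomial check in SAP 5.2, fitted in the ordinary way on 44 homes, has a false-positive rate of about 9–11% instead of 5%

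*SAP*

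**What the plan says.** SAP 5.1.2 analyses the primary endpoint at nursing-home level with a Poisson regression containing "group (intervention vs control) as independent variable, realized follow-up time as offset, region of NHs and the respective baseline hospitalization rate as covariates". It has no term for variation between homes beyond Poisson. Section 5.2 adds, for this endpoint, that "an evaluation with the negative binomial distribution to detect a possible but not expected overdispersion will be performed".

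Section 2.1 reports "44 nursing homes with an average of 96 residents each". These homes are spread over four centres with two regions apiece, which makes 8 regions. Section 3.1 sets the error rate: "All applicable statistical tests will be two-sided and at a 5% significance level", with 95% intervals throughout.

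Section 5.2 does not say how the negative binomial dispersion is estimated, which reference distribution is used, or whether a small-sample correction applies. Section 5.5 lists software packages but no command or option.

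**The concern.** A negative binomial model is a reasonable response to overdispersion, but its default fit relies on large samples. Maximum likelihood estimates the dispersion without allowing for the coefficients fitted in the mean, and the usual test then refers the estimate to a normal distribution. With many homes this would not matter. Here roughly 10 coefficients are fitted to 44 counts, one per home. The residual variance is therefore understated, and z is used where t on 34 degrees of freedom is needed.

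This is the one analysis in the SAP designated for overdispersion. If the Poisson result is significant and homes do vary, readers will look to it to see whether the finding survives. A check that rejects at nearly twice its stated level in that situation could make a fragile result look robust.

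**Working it through.** **Inputs from the SAP**
- Units: 44 homes, 22 per group (2.3).
- Regions: 4 centres × 2 = 8 (2.1), so 7 contrasts when region is a fixed covariate (5.1.2).
- Coefficients: 1 intercept + 1 group + 7 region + 1 baseline rate = 10.
- Residual degrees of freedom: 44 − 10 = 34.
- Test level: two-sided 5% (3.1).

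**Closed form**
1. Standard-error scale without the correction: √(34/44) = 0.879, so 12.1% too small.
2. Interval width relative to a proper t interval: (1.960 × 0.879)/2.032 = 0.848, so 15.2% too narrow.
3. False-positive rate: P(|t₃₄| > 1.960 × 0.879) = P(|t₃₄| > 1.72) = 9.4%.

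**Simulation under no treatment effect**

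The SAP gives neither the hospitalization rate nor the between-home variation, so these are assumptions: 50, 80 or 120 hospitalizations per 100 resident-years, and a coefficient of variation (CV) of the home effect from 0 to 0.5. Each trial had 44 homes in 8 regions, near-1:1 allocation within region, sizes around 96 residents, and log size as offset in place of follow-up time. There were 4,000 trials per row, so the simulation standard error is about √(0.095 × 0.905/4000) = 0.5 percentage points. Mixing was gamma except in the last row.

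| CV | Rate per 100 | Negative binomial, Wald | Likelihood ratio | Mean SE / true SD | Width vs t₃₄ interval | Negative binomial, corrected, t₃₄ | Primary Poisson |
|---|---|---|---|---|---|---|---|
| 0 | 80 | 4.8% | 4.6% | 1.011 | 0.975 | 3.2% | 4.9% |
| 0.1 | 80 | 10.3% | 9.8% | 0.855 | 0.825 | 5.1% | 18.9% |
| 0.2 | 80 | 9.6% | 8.7% | 0.874 | 0.843 | 5.1% | 37.2% |
| 0.3 | 80 | 9.2% | 8.3% | 0.870 | 0.839 | 4.6% | 52.3% |
| 0.4 | 80 | 9.6% | 8.4% | 0.864 | 0.833 | 5.3% | 62.3% |
| 0.5 | 80 | 9.8% | 8.4% | 0.862 | 0.831 | 5.9% | 68.7% |
| 0.3 | 50 | 9.5% | 8.5% | 0.869 | 0.838 | 5.1% | 42.6% |
| 0.3 | 120 | 10.2% | 9.0% | 0.852 | 0.822 | 5.5% | 58.3% |
| 0.3, lognormal | 80 | 10.1% | 9.2% | 0.845 | 0.815 | 5.8% | 51.7% |

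In the corrected column the dispersion is chosen so that the Pearson chi-square equals 34.

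A second set of 2,000 null trials in each of 8 settings (60 or 100 per 100 resident-years, CV 0.1–0.4) gave 9.3–11.0% for the ordinary Wald test, with mean SE 0.84–0.88 of the true SD. Poisson with Pearson dispersion and t₃₄ gave 5.3–6.4% there. A further 1,500 trials in each of two settings gave 6.1% and 5.9% for the Pearson-calibrated negative binomial.

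The nominal 5% is reproduced when counts are purely Poisson. Once there is extra variation the rate goes to 9–11% and stays there across the assumed rates, CVs and mixing distributions, as expected if 10 coefficients on 44 units are the cause.

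**The case against.** The strongest reply is that the SAP does not commit to maximum likelihood with a z test. It names only the distribution, and a competent analyst might apply a correction. This stands in part: a reader might infer that the plan prescribes a faulty fit, and it does not. But an unqualified negative binomial regression ordinarily means that fit, and the SAP's stated purpose is to specify the methods further. Using the likelihood-ratio test instead does not cure the problem (8.3–9.8% with overdispersion).

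Second, a reader might infer that the check always runs near 10%. It does not: with no overdispersion, which the SAP says it does not expect, it holds about 5%. The fault appears only in the case the check exists for.

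Third, it would be too much to say that nothing else in the plan touches between-home variation. The Covid-19 analysis in 5.4.2 is a mixed Poisson model with a random intercept for the home. It pools t0, t1 and t2, has a different stated aim, and does not cover variation specific to a home and period, so it is at most a partial check.

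Fourth, no decision rule hangs on this p-value. The confirmatory test is the Poisson model, and because the inflation is two-sided, a false favourable result from the check occurs about 5% of the time against a nominal 2.5%. Under the same overdispersion the primary Poisson test rejects 19–69% of the time, so the check removes most of that error. This stands, and it makes the point secondary to the primary model. It does not remove the point: promoting the 5.2 model to primary, as fitted by default, would still leave an error rate near 10%.

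Finally, the count of 10 depends on region being a fixed covariate. Section 5.1.2 lists "region of NHs and the respective baseline hospitalization rate as covariates", whereas the resident-level models in 5.1.3 use random intercepts, so this is the natural reading. Dropping region is not an obvious way out, since 2.2 describes "A 1:1 cluster-randomization at the level of NHs stratified by study center and region".

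**Conclusion.** The concern holds conditionally. If homes vary beyond Poisson and the 5.2 model is fitted in the ordinary way, standard errors are about 12–16% too small, 95% intervals about 15–18% narrower than a t₃₄ interval, and the two-sided false-positive rate about 9–11%. The standard-error and width figures should be kept apart, because the width also carries the z-for-t substitution.

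Three assumptions underlie this: the default estimator, which the SAP does not name; region as 7 fixed contrasts; and the assumed event rates and CVs, to which the result is insensitive. It merits a change because the affected analysis is the one designated for overdispersion. The larger weakness is the primary Poisson model itself.

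**What to change.** State in 5.2 that the overdispersion analysis uses a dispersion estimate corrected for degrees of freedom and a t reference on 34 degrees of freedom. Either of two forms will do:
- a negative binomial model with the dispersion set so that the Pearson chi-square equals its 34 residual degrees of freedom; or
- the Poisson model with Pearson dispersion on 34 degrees of freedom, not allowed below 1.

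Both bring the false-positive rate to about 5–6.5% in the settings examined, so the choice between them is a matter of preference. If the final number of homes or regions in the model differs, the 34 should be recomputed.

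The cost is one sentence in the SAP and a few lines of code. The sensitivity interval becomes about 15–20% wider (closed form 1/0.848 = 1.18), and the test is slightly conservative, at about 3–4%, when there is no overdispersion. The design and the data collection do not change.

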## b. AND honored:

- i. "ostensible" preferences (independent of any underlying SDM process) were honored (yes vs. no)
- ii. "informed" preferences (at least the 2nd step of the SDM process was reached) were honored (yes vs. no)
- iii. "enabled" preferences (at least the 3rd step of the predefined 4-step SDM process was reached) were honored (yes vs. no)
- iv. "empowered" preferences (at least the 4th step of the predefined 4-step SDM process was reached) were honored (yes vs. no),

continuously over the 12 months before t2.

- 11. Perception of care consistency in residents deceased during the observation period measured as judgement (Likert Scale 0-10) of
  - a. proxies and

- b. nurses, respectively, whether medical care (F2a) and nursing care (F2b) delivered in the past 3 months before death was consistent with the residents' then care preferences, measured by key items F2a/F2b selected from the After Death Bereaved Family Member Interview (ADBI) and documented continuously over the 12 months before t2.
- 12. Shared decision making and Advance Care Planning in residents deceased during the observation period, observed in the 3 months prior to death, and measured by means of the corresponding sections of an adapted German version of the After Death Bereaved Family Member Interview (ADBI):
  - a. Inform and promote shared decision making (problem score #2)
  - b. Encourage advance care planning (problem score #3)
  - c. Overall Rating Scale for patient focused, family centered care
- 13. number of hospitalizations per 100 residents per last 12 months at t2
- 14. number of total hospital days per 100 residents per last 12 months at t2
- 15. number of visits at hospital outpatient services per 100 residents per last 12 months at t2
- 16. number of attempted CPRs in hospital or EMS per 100 residents per last 12 months at t2
- 17. number of intensive care unit days per 100 residents per last 12 months at t2
- 18. proportion of residents with artificial ventilation in hospital or EMS at t2
- 19. number of invasive ventilation hours in hospital per 100 residents per last 12 months at t2
- 20. proportion of residents with PEG in place at t2
- 21. proportion of residents with newly inserted PEG at t2
- 22. proportion of residents with PEG in use at t2
- 23. mortality rate during the observation period before t2
- 24. place of death (nursing home vs. others) during the observation period before t2

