## 2.7 Timing of outcome assessments

The timeline of the BEVOR study is as follows (see Fig. 2 of the study protocol): at the start of the study, data collection is initiated, which corresponds with the baseline measurement (t0). At the end of the run-in phase of the intervention, the 12-month observation phase begins (t1). The end of the observation phase corresponds with the measurement at 12-months follow-up (t2). The run-in phase of the intervention describes the time in which the intervention is established and reaches the residents, the NHs and the regions. It lasts from the time of randomization until t1. The intervention itself continues during the observation period.

The 12 months observation period's data will be collected in one follow up collection (DC1) or, respectively, for DC2 continuously over the entire period, including

- interviews with relatives and nursing home staff of deceased residents,
- four three-monthly sessions to identify all potentially life-threatening events and related treatment decisions for the respective preceding 3 months (3CP data collection including interviews), as appropriate.

The start of the observation phase (t1) is fixed for all study centres at 01.09.2021.

**NH level (DC1):** All outcomes on NH level will be measured at t0, t1 and t2 for the preceding 12 months.

**Resident's level (DC2):** Data collection 2 is performed with residents, their surrogates and/or relatives, and the respective nursing staff and contains three different sections with different time points:

- 1. Framework survey including quality of care survey is conducted at t0 and t2 for the 12 months observation period.
- 2. Care consistency with care preferences (3CP) is assessed at t0 for the preceding 3 months and at t2. Data collection at t2 will be splitted into 4 phases of the 12-months observation period (each covering the preceding 3 months), beginning 3 months after t1, to collect data over the twelve months of observation as accurately as possible. It is ensured that there is no overlap in the survey periods.
- 3. The survey of relatives and staff regarding deceased residents is conducted at t0 and continuously over the 12 months before t2.

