## 3.2 Adherence and protocol deviations

Major protocol violation includes ineligible NHs and residents who were included in the trial by mistake, or for whom the intervention or other procedure differed from that outlined in the protocol, or failure of consent process.

Protocol violations are defined as deviations from the planned procedure according to the study protocol for which the study team is responsible. Major protocol deviations occur if

- the ACP facilitator does not attend the NH as scheduled
- data collection could not be performed (e.g. due to covid-19 pandemic)
- in- or exclusion criteria are violated (for both, residents and NHs)
- residents move out of the participating NH

Absence of sufficient adherence from the intervention according to the study protocol is defined at the NH and residents level. A major adherence deviation occurs if

- NHs of the intervention group do not utilize a minimum of the intervention elements (e.g. meetings of institutional steering group, staff qualification, ACP-facilitation, information of residents, relatives and surrogates), the minimum being defined as an intervention load amount below the respective median of all NHs in the intervention group

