## 4.5 Characteristics of participating NHs and residents

The following descriptive characteristics are measured at t0 and, at NH level, additionally at t1:

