# 5 Analysis

### 5.1 Analysis methods

## 5.1.1 Descriptive analysis of baseline characteristics

For baseline characteristics (as defined in 4.5) descriptive statistics will be presented separately for the two treatment groups, i.e. intervention and control, on NH level as well as on resident level. Categorical data are summarized by absolute and relative frequencies. Continuous data are summarized by mean and standard deviation (SD) as well as median, quartiles and/or interquartile range (IQR), as appropriate. The number of available observations or the number of missing observations are reported separately for treatment groups. On resident level, statistical comparisons using Mann-Whitney U-test, Chi²-test or t-test (according to the data type of the characteristics) will be used to identify any imbalances between the two study groups. On NH level, statistical comparisons are not performed due to randomization.

On resident level, responders and non-responders will be compared descriptively regarding care level, age and sex.

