### NH level:

- Occupied bed days (in the past 12 months)
- Sex ratio of residents
- Mean age of residents
- Rate of all deceased residents (in the past 12 months)
- Rate of full nurse equivalents per 100 residents
- Rate of palliative care qualified nurses per 100 residents
- Rate of general practitioners per 100 residents

SAP **V01-00** 

- Defined private co-payment for residents (relative deviation from the regional mean)
- Total sick leave days per nursing staff (i.e. number of registered/assistant/hired nurses) (in the past 12 months)

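### The adjusted analysis in SAP 5.2 selects covariates by p-value at two time points under an unfixed rule, may adjust for post-randomisation nursing-home values, and needs tests that SAP 5.1.1 says are not done

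*SAP*

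**What the plan says.** SAP 5.2 closes its list of sensitivity analyses with this rule: "an adjusted analysis is performed taking into account remarkable (p < 0.05) differences at baseline and t1, regarding the following potential confounders". Nine candidates follow at nursing-home (NH) level and five at resident level. The sentence names no endpoint; the one before it covers the primary and key secondary endpoints.

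Four other places bear on the rule:

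- **Timing of measurement (SAP 4.5).** "The following descriptive characteristics are measured at t0 and, at NH level, additionally at t1". Resident characteristics are therefore available at t0 only.
- **Position of t1 (SAP 2.7).** On the run-in: "The run-in phase of the intervention describes the time in which the intervention is established and reaches the residents, the NHs and the regions". On its length: "It lasts from the time of randomization until t1".
- **Testing (SAP 5.1.1).** Tests are named for resident characteristics. For homes: "On NH level, statistical comparisons are not performed due to randomization".
- **Primary model (SAP 5.1.2).** Group, region and baseline hospitalisation rate, with follow-up time as offset. No covariate is chosen by p-value.

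**The concern.** There are three separate problems.

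1. **The rule is not fixed.** A variable could qualify by differing at t0, at t1, at either or only at both, and either value could then be entered. Screening on group differences needs the group labels, so these choices would be settled after unblinding. The SAP's introduction says the document is finalised before that.
2. **NH-level t1 values are post-randomisation.** Some candidates lie close to what the programme does or aims at, so adjusting for their t1 values may remove part of its effect.
3. **The tests are not planned.** The NH-level screen in 5.2 relies on comparisons that 5.1.1 says are not made, and no NH-level test is named.

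At stake is how the adjusted result can be read. If it differs from the primary result, the cause could be confounding, chance selection or adjustment for a programme effect, and the plan offers no way to tell these apart. Two analysts following 5.2 could also fit different models.

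**Working it through.** The SAP states no figure for this rule, so there is nothing to reproduce. The first step compares the texts; the others gauge size under assumptions.

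**1. Which candidates might the programme change by t1?**

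- Death rate: the candidate is "Rate of all deceased residents (in the past 12 months"); secondary outcome 23 in SAP 1.2.2 is "mortality rate during the observation period before t2".
- Nurses with a palliative qualification: SAP 3.2 gives as intervention elements "meetings of institutional steering group, staff qualification, ACP-facilitation, information of residents, relatives and surrogates".
- Staff sick leave: SAP 1.1 names a lower emotional burden on staff as an aim.
- Sex ratio, mean age and private co-payment are unlikely to be changed by the programme.

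**2. Chance selection with no true difference.** From the SAP: 44 homes, 22 per group (2.3), eight regions (2.1), stratified allocation (2.2), nine NH candidates (5.2), two-sided 5% level (3.1). For nine independent variables at one time point:

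1 − 0.95^9 = 0.37

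This ignores stratification by region, which balances the groups and makes an unadjusted test conservative. A simulation with 20,000 runs per cell allows for it. Assumptions: four regions of six homes and four of five, near-balanced allocation within region, unadjusted two-sample t-tests.

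| Chance that at least one of nine is selected | Region explains 0% of variance | 10% | 30% | 50% |
|---|---|---|---|---|
| One time point, independent variables | 37% | 31% | 21% | 11% |
| One time point, variables correlated 0.3 | 33% | 28% | 18% | 10% |
| Either time point, t0–t1 correlation 0 to 0.9 | 60–48% | 52–42% | 37–29% | 21–17% |
| Both time points, t0–t1 correlation 0 to 0.9 | 2–23% | 2–20% | 1–12% | 0–6% |

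For one time point, 37% is thus an upper-end figure. These percentages show how unstable the model choice is; they do not measure bias.

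**3. A variable shifted at t1 only.** Same layout, one variable, region share 0 to 50%, t0–t1 correlation 0.5 to 0.9 (assumed):

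| Shift at t1 | Selected if either suffices | Selected if both are required |
|---|---|---|
| 0.25 SD | 8.7–16.5% | 0.3–2.7% |
| 0.5 SD | 36.5–40.0% | 0.6–2.5% |

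The reading of one word changes the selection probability severalfold.

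**4. Effect on the incidence rate ratio if a shifted t1 value enters.** On the log scale, let the total effect be τ + b·d. Here d is the programme's shift of the covariate in SD, and b is the covariate's association with hospitalisation per SD. Adjusting for the t1 value leaves τ, so the ratio moves by exp(b·d). With assumed d of 0.25 to 0.5 and b of 0.05 to 0.20:

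- exp(0.25 × 0.05) = 1.013
- exp(0.5 × 0.10) = 1.051
- exp(0.5 × 0.20) = 1.105

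For a t0 value the expected group difference is zero by randomisation, so no such expected shift arises.

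**5. The screen as a detector.** With 22 homes against 22 and no allowance for region, a true 0.5 SD difference reaches p < 0.05 with probability of about 0.38 (0.3 SD: 0.17; 0.8 SD: 0.76). The rule therefore also misses most moderate imbalances.

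**The case against.** The strongest reply is that the text joins the two time points with *and*. Read literally, a variable must already differ at t0, before the programme could act, and step 3 then puts selection of a purely t1-shifted variable at 3% or less. This stands as far as it goes. But the SAP does not fix that reading, and even under it a variable selected by chance at t0 could enter with its t1 value.

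The links to the programme are inferred. Outcome 23 is a resident-level outcome in the observation period, while the candidate is an NH-level rate over the preceding 12 months. The palliative qualification in SAP 5.4.1 is not stated to come from the programme's training. The staff aim does not mention sick leave. All of this stands, which is why the bias is a risk and not a demonstrated fact. The shift d and association b are assumed, and the primary model's covariates would probably reduce b. Weighting step 4 by the *either* selection probabilities gives an average factor of about exp(0.09 × 0.0125) = 1.001 to exp(0.40 × 0.10) = 1.04.

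Section 5.1.1 can also be read as governing only the descriptive tables, with 5.2 as an exception. That is possible. But 5.1.1 refers to the characteristics defined in 4.5, which include the t1 measurements. Its stated reason, randomisation, applies equally to a screen at t0.

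At resident level the timing and the tests are clear, so the first two problems and the missing tests concern NH level only. Finally, a single clarifying clause would cure the ambiguity. It would not cure selecting covariates on chance differences in a randomised trial, nor the possible entry of post-randomisation values.

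**Conclusion.** The concern holds. The NH-level rule does not determine one model, it can admit post-randomisation values, and it relies on tests the plan says are not performed. The selection probabilities rest on the assumed layout and correlations. The factor of 1.01 to 1.11 rests on assumed shifts and associations and applies only if a t1 value that the programme changed is entered. No bias is demonstrated, and the risk differs across the nine variables.

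The consequence is confined to the reported adjusted sensitivity analysis. The primary model in SAP 5.1.2 is untouched, and the possible extension to other secondary endpoints in SAP 5.4.3 is kept out of the study report. The change should be made because readers will use this analysis to judge how robust the result is.

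**What to change.** Replace the sentence in SAP 5.2 with wording such as:

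> An adjusted sensitivity analysis adds a fixed set of t0 covariates from the lists below, named before unblinding on prognostic grounds and entered regardless of observed group differences. t1 values are reported descriptively only.

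The sponsor chooses the set and should name the endpoints it applies to. Blinded pooled baseline data can inform the choice, as they did for the key secondary endpoints (SAP 1.2.2). Dropping the significance screen also reconciles 5.2 with 5.1.1.

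The Covid-19 question keeps its own model over t0, t1 and t2 (SAP 5.4.2). That model contains none of the nine covariates. If adjustment for conditions at the start of observation is still wanted, specify a separate model, state which value enters, and label it as post-randomisation adjustment.

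The cost is SAP wording and a few degrees of freedom. With 44 homes, the primary model leaves 44 − 1 (intercept) − 1 (group) − 7 (eight regions) − 1 (baseline rate) = 34 residual degrees of freedom. Three added NH covariates leave 31; all nine would leave 25.
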